14.10 PARTICIPANT QUESTIONNAIRES

Participant-reported steroid dose, and whether this needed to be increased due to increase in PMR symptoms, will be collected via the Steroid Use Questionnaire. This questionnaire will be administered every four weeks from week 4 to week 80. Cumulative (prednisolone-equivalent) steroid dose will be estimated from data provided in the Steroid Use Questionnaire, interpolating if necessary. PMR relapse date(s) and date(s) of steroid cessation, if applicable, will be calculated from the data provided in the Steroid Use Questionnaire, allowing time to relapse, number of PMR relapses and time to steroid cessation and time to steroid-free remission to be calculated during the analysis of the trial.

PMR symptom severity will be captured via the PMR-IS administered at baseline (week 0) and weeks 12, 24, 36, 48, 60, 72 and 80 post randomisation.

Participant health related quality of life will be captured via the EQ-5D-5L questionnaire. This will be administered at baseline (week 0) and weeks 12, 24, 36, 48, 60, 72 and 80 post randomisation.

Participant healthcare resource use will be collected at baseline (week 0), and weeks 12, 24, 36, 48, 60, 72 and 80 post randomisation.

In addition, questionnaire booklets at baseline (week 0) and weeks 24 and 80 post baseline will include a Visual Analogue Scale (range 0 to 100mm) on which participants will mark the level of Pain they experience.

This will be used to score the PMR Activity Score. Booklets including this VAS will be distributed separately, as professional printing is required to ensure VAS lengths are exactly 100mm.

Questionnaires completed at baseline (week 0) will be administered by the research staff via a paper booklet before the participant has been informed of the randomisation allocation. Participants will be given the choice of completing questionnaires at all subsequent time points either on paper or electronically. For participants wishing to complete the questionnaires electronically they will be given the option of receiving an email or text message with a link to their questionnaire. Participants' preferred method of questionnaire administration and completion will be collected during the trial randomisation process and applicable contact details, postal address/email address/mobile phone number, collected. The CTRU will send questionnaires to participants directly. Non-respondents will receive reminders by their pre-stated preferred method of communication. The CTRU will contact sites at intervals throughout the study to ensure that consenting participant's contact details and status have not changed and that it is still appropriate to send them a questionnaire.

14.11 DEATHS

All deaths must be recorded on the Notification of Death eCRF and submitted to the CTRU within 7 days of notification to the site trial research team.

All deaths should be assessed to determine whether they meet the criteria of a SAE, SAR or SUSAR. Definitions and reporting requirements for SAEs, SARs and SUSARs can be found in Section 15 of the protocol.

14.12 PARTICIPANT WITHDRAWAL

The PI or delegate should ensure that the specific wishes of any participant who wishes to withdraw consent for further involvement in the trial, be that from further treatment and/or follow-up data collection, are defined and documented using the Withdrawal eCRF in order that the correct processes are followed by the CTRU and site following the withdrawal of consent.

If a participant withdraws consent for further trial treatment and / or further collection of data, their data collected prior to withdrawal of consent will remain on file and will be included in the final study analysis. Data outstanding up to the point of withdrawal will be chased with site. The Participant will be asked to sign a withdrawal of consent form.

It should be made clear to any participant specifically withdrawing consent for further data collection that data pertaining to safety, for example SAEs and SUSARs, will continue to be collected for regulatory reporting purposes and will be included in any safety analysis. In addition, it is suggested that the participant is made aware of the fact that if any significant new information becomes available in regard to the treatment they have received in the trial it may be necessary to contact them in the future.

Where the participant withdraws their consent for completion of participant questionnaires, questionnaires completed prior to withdrawal of consent will be included in the analysis.

If it is the decision of the attending clinician to withdraw the participant from further treatment, then this should also be documented on the Withdrawal eCRF. The trial Schedule of Events and data collection should continue per protocol, unless the participant explicitly withdraws their consent for this.

14.13 PARTICIPANT TRANSFERS

If a participant is being permanently transferred to another site participating in STERLING, then the Participant Transfer eCRF needs to be completed and returned to CTRU as soon as possible to enable appropriate tracking of the participant.

Copies of any paper CRFs, consent forms and any other relevant correspondence is sent to the new hospital, with the originals kept at the original enrolling site. Data queries from events arising before the date of transfer will be directed to the original enrolling site; data queries from events arising after the transfer date will be directed to the new site. Both sites must ensure that the participant transfer is recorded on the participant log in the Investigator Site File.

14.14 PROTOCOL VIOLATIONS

A protocol violation can be defined as: Any accidental or unintentional change to, or non-compliance with the protocol that increases risk or decrease benefit, or has a significant effect on the participant's rights, safety, or welfare, or on the integrity of the data.

Examples of a violation include, but are not restricted to:

- Failure to obtain valid informed consent prior to performing any other trial investigation or procedure.
- Breaches of eligibility criteria.
- Drug administration errors relating to the IMP (e.g. overdose, underdose, not performing specified suitability-for-treatment tests, not modifying dose in line with required modifications).

Protocol violations should be reported immediately to the CTRU using the Protocol Violations eCRF.

The following events do not need to be reported as a protocol violation:

- A rescheduled study visits
- Participant refusal to complete scheduled research activities
- Limited dosing errors by either participant or site, i.e. 1 or 2 that did not result in an SAE and that were deemed not medically significant by site.

Contact details for reporting protocol violations (before or after eCRF entry):

Email: [contact]

14.15 DEFINITION OF END OF STUDY

The end of the trial is defined as the date of the collection of the last participant's last data item.

Participants will be followed up until death or until the end of their follow-up period as described in Section 14.6-14.10 (whichever is sooner).

15 PHARMACOVIGILANCE

15.1 GENERAL DEFINITIONS

Adverse Event (AE) - An adverse event (AE) is any untoward medical occurrence in a participant or clinical trial subject administered a medicinal product and which does not necessarily have a causal relationship with this treatment.

Adverse Reaction (AR) - All untoward and unintended responses to an investigational medicinal product related to any dose administered. This definition implies a reasonable possibility of a causal relationship which is supported by facts, evidence or arguments to suggest a causal relationship. This definition includes ARs resulting from a medication error and uses outside what is foreseen in the protocol, including misuse and abuse from the product.

N.B. Medication errors themselves, or misuse/abuse of trial treatment should be notified to CTRU via a protocol violation.

Serious Adverse Event (SAE) - Any untoward medical occurrence or effect that at any dose:

- results in death
- is life-threatening
- requires hospitalisation or prolongation of existing hospitalisation
- results in persistent or significant disability or incapacity
- is a congenital anomaly or birth defect
- jeopardised the subject or required intervention to prevent one of the above - hereinafter referred to as 'important medical events (IME)'

Medical and scientific judgement must be exercised in deciding whether an event is serious (see section 15.6 for Responsibilities). These characteristics / consequences must be considered at the time of the event and do not refer to an event which hypothetically may have caused one of the above. For example, life threatening: this refers to an event in which the subject was at risk of death at the time of the event; it does not refer to an event which hypothetically might have caused death if it were more severe.

Serious Adverse Reaction (SAR) - reference is made to the criterion of 'Seriousness' above in relation to SAE. (Any suspected transmission via a medicinal product of an infectious agent is also considered a serious adverse reaction.)

Suspected Unexpected Serious Adverse Event (SUSAR) – a SAR, the nature and severity of which is not consistent with the Reference Safety Information (RSI).

Severity describes the intensity of the event. This must be distinguished from the term 'serious'.

Reference Safety Information (RSI) - When determining whether an SAE is expected or not, please refer to section 4.8 of the pharmacovigilance reference copy of the methotrexate or leflunomide (as relevant) Summary of Product Characteristics (SmPC) supplied by CTRU and included in the Investigator Site File. Events appearing in the RSI should be recorded as SARs on the SAE CRF and not as SUSARs, unless the nature, seriousness, severity or outcome is not consistent with the relevant product information.

15.2 OPERATIONAL DEFINITION & REPORTING ADVERSE EVENTS/REACTIONS (AES/ARS)

Information about adverse events/reactions whether volunteered by the participant, discovered by investigator questioning or detected through physical examination, laboratory test or other investigation will be collected and recorded on the relevant Clinical Assessment CRF. All adverse events should be recorded in the participant's medical notes so that they can be followed up if necessary.

This is a randomised controlled trial using treatments with well-known safety profiles already established in the therapy of rheumatological conditions. Although not licensed for PMR, MTX has been shown in clinical practice to be safe and well-tolerated in a PMR population (31). Similarly, in the previous trial by Caporali et al., the main adverse effects that occurred more often in the MTX than placebo arm of the trial was mild gastrointestinal adverse effects. The strategy being tested is DMARD (MTX or LEF) in conjunction with usual care steroid taper, compared to usual care steroid taper alone. The IMPs are defined as the DMARDs, MTX or LEF.

Therefore, the following expected adverse events, related to either tapering of steroid for PMR or to the IMPs, will be reported. It is noted that causality (determination that an Adverse Event is an Adverse Reaction related to a particular IMP) may be difficult to determine since participants will also be receiving other medications, including steroids which should not be stopped abruptly and which can cause many of the adverse events listed below; however, because MTX is administered weekly, assessment of causality may be facilitated by temporality of symptoms in relation to MTX administration

15.2.1 Expected AEs potentially related to tapering of steroid for PMR:

- Diagnosis of adrenal insufficiency – see section 17.2.2
- Diagnosis of giant cell arteritis

15.2.2 Expected AEs/ARs potentially related to MTX:

Please report the following if severity is consistent with **CTCAE grade 2 and above (see Appendix 3)**:

- Clinically significant deranged liver function test values (as judged by the local investigator)
- Clinically significant cytopenia (as judged by the local investigator)
- Depression (diagnosis of depression, or initiation or increase of depression medication)
- Infection (infection requiring treatment with oral, IV or IM antibiotics, or any episode of shingles, or a positive community test for COVID-19)
- Mucositis oral (participant reported)
- Nausea (participant reported)
- Abdominal pain (participant reported)
- Diarrhoea (participant reported)
- Hair thinning/alopecia (participant reported)
- Headache (participant reported)
- Fatigue (participant reported)

15.2.3 Expected AEs/ARs potentially related to LEF:

Please report the following if severity is consistent with **CTCAE grade 2 and above (see Appendix 3)**:

- Clinically significant deranged liver function test values (as judged by the local investigator)
- Clinically significant cytopenia (as judged by the local investigator)
- Hypertension (requirement for new antihypertensive medication or increased dose of current antihypertensive medication)
- Infection (infection requiring treatment with oral, IV or IM antibiotics, or any episode of shingles, or a positive community test for COVID-19)
- Mucositis oral (participant reported)
- Nausea (participant reported)
- Abdominal pain (participant reported)
- Diarrhoea (participant reported)
- Hair thinning/alopecia (participant reported)
- Paraesthesia (participant reported)
- Rash maculo-papular (participant reported)
- Headache (participant reported)
- Fatigue (participant reported)

These should be reviewed and classed by a clinically qualified person to assess for causality and expectedness.

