5.3 THE NEED FOR BETTER TREATMENT OPTIONS FOR PMR

Glucocorticoid (“steroid”) therapy rapidly brings the pain and stiffness of PMR under control, with a corresponding improvement in physical and mental health-related quality of life compared to untreated PMR (14). However, steroid therapy has multiple unwanted effects (steroid toxicity), which accumulate over time and may not be fully reversible even after the steroid treatment has stopped (15). Older patients such as those with PMR are particularly susceptible to steroid toxicity. Patients whose duration of prednisolone therapy has been prolonged by dose-escalations related to PMR relapses are likely to be at the greatest risk of long-term steroid toxicity.

Steroid treatment for PMR confers a 63% increased risk of fracture (16), at least a twofold increased risk of diabetes(17) and a dose-dependent increased risk of infection (18). The risk of infection is related to both current and cumulative dose. Prolonged steroid therapy (daily dose of 5mg prednisolone-equivalent or greater, for 4 weeks or more) can cause adrenal insufficiency that may persist for months to a year or more after the steroid dose is tapered below 5mg daily (19)

Other outcomes of glucocorticoid therapy listed in the Outcome Measures in Rheumatology Clinical Trials (OMERACT)-endorsed Core Domain Set for adverse impacts of glucocorticoid therapy include weight gain, mood disturbance, and fatigue (20). 15% of patients with PMR are reported to experience depression (21) which is likely to represent the combined effect of the disease and the treatment.

An adjunctive treatment that could reduce steroid requirements in relapsing PMR would have the potential to substantially improve long-term physical and mental health of this patient group.

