15.3 OPERATIONAL DEFINITION - SERIOUS ADVERSE EVENTS/REACTIONS (SAEs/SARs)

It is acknowledged that this patient group are likely to experience numerous adverse events related to co-morbidities other than PMR or its treatment. In acknowledgement of this and the well-known safety profile of DMARDs, in this study only serious adverse events that are suspected to be related to PMR or the IMPs will be reported.

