As for the primary outcome, if any steroid medications other than prednisolone are prescribed, these will be converted to an agreed “prednisolone equivalent dose” prior to analysis.

Safety

Adverse events (AEs) of Special Interest reported over 18 months post randomisation will include those relevant to PMR and/or investigational medicinal product.

Serious adverse events (SAEs) and SUSARs regardless of relationship to PMR or investigational product reported over 18 months post randomisation.

Glucocorticoid toxicity

Glucocorticoid toxicity is defined as per the OMERACT Glucocorticoid Core Domain Set (infection, diabetes, hypertension, fracture) adapting measures from the Glucocorticoid Toxicity Index (67)

Time to development of GCA

Time to development of GCA (defined as rheumatologist-confirmed and treated according to GCA treatment protocols specified in 2020 BSR guideline, without the diagnosis later being revised from GCA during the 18 month period) will be defined as the duration between randomisation and date of GCA diagnosis. Participants who are not diagnosed with GCA during follow-up will be censored at 18 month, or else at date of death or withdrawal.

Proportion of participants diagnosed with adrenal insufficiency

The proportion of participants who are identified as diagnosed with adrenal insufficiency will be the proportion of participants who either have a low value of 9am cortisol test, or an intermediate value followed by a positive short synacthen test, at any point during follow-up. Adrenal insufficiency screening tests (9am cortisol) will be conducted within the trial but confirmation of physician diagnosis of adrenal insufficiency, will be recorded, along with the relevant date and actions taken in response.

Deaths

Deaths from all causes over 18 months post randomisation. Date of death will be recorded, and time to death will be derived as days from randomisation to death.

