For most purposes of the conduct and the analysis of the trial, inhaled, intranasal and topical glucocorticoids (steroids) will be assumed to be equivalent to 0mg oral prednisolone.

It should be noted that there is a risk that prolonged or repeated treatment with non-oral glucocorticoid, particularly fluorinated compounds, could contribute to glucocorticoid toxicity including the potential for iatrogenic adrenal insufficiency.

APPENDIX 2

Birth control methods which may be considered as highly effective

For the purpose of this protocol, methods that can achieve a failure rate of less than 1% per year when used consistently and correctly are considered as highly effective birth control methods.

- combined (oestrogen and progesterone containing) hormonal contraception associated with inhibition of ovulation:
 - oral
 - intravaginal
 - transdermal
- progesterone-only hormonal contraception associated with inhibition of ovulation:
 - oral
 - injectable
 - implantable
- intrauterine device (IUD)
- intrauterine hormone-releasing system (IUS)
- bilateral tubal occlusion
- vasectomised partner ³
- sexual abstinence ⁴

³ Vasectomised partner is a highly effective birth control method provided that partner is the sole sexual partner of the trial participant and that the vasectomised partner has received medical assessment of the surgical success.

⁴ In the context of this guidance sexual abstinence is considered a highly effective method only if defined as refraining from heterosexual intercourse during the entire period of risk associated with the study treatments. The reliability of sexual abstinence needs to be evaluated in relation to the duration of the clinical trial and the preferred and usual lifestyle of the subject.

APPENDIX 3

Common Terminology Criteria For Adverse Events (CTCAE)

Events will be graded according to the National Cancer Institute Common Terminology Criteria for Adverse Events V5.0 (NCI-CTCAE). A copy is provided in the Investigator Site File and may be obtained at:

https://ctep.cancer.gov/protocolDevelopment/electronic_applications/docs/CTCAE_v5_Quick_Reference_8.5x11.pdf

Published: November 27, 2017

REFERENCES

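### The reportable-infection item omits infections managed without antibiotics (other than shingles and community-test COVID-19), conflicts with its own grade 2 header, and is not reliably backed up by the SAE rules

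*Protocol*

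**What the plan says.** Section 15.2 begins broadly: information on adverse events "will be collected and recorded on the relevant Clinical Assessment CRF". It then limits what is reported to a list of expected events for steroid tapering, methotrexate and leflunomide.

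The methotrexate list (15.2.2) and the leflunomide list (15.2.3) open with the same instruction, "Please report the following if severity is consistent with" "CTCAE grade 2 and above (see Appendix 3"). Under it, in identical words in both lists, stands "Infection (infection requiring treatment with oral, IV or IM antibiotics, or any episode of shingles, or a positive community test for COVID-19"). Appendix 3 names the grading system, "Events will be graded according to the National Cancer Institute Common Terminology Criteria for Adverse Events V5.0 (NCI-CTCAE"), but does not reproduce the grade descriptions.

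Infection or serious events also appear in these places:

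- Section 15.1 treats any event that is life-threatening or leads to or prolongs a hospital stay as an SAE, whatever its cause.
- Section 15.3 narrows this: "only serious adverse events that are suspected to be related to PMR or the IMPs will be reported".
- Section 16.2.2 (Safety) counts SAEs over 18 months whether or not they are related to PMR or the trial drugs.
- Section 16.2.2 (Glucocorticoid toxicity) states: "Glucocorticoid toxicity is defined as per the OMERACT Glucocorticoid Core Domain Set (infection, diabetes, hypertension, fracture"), with measures adapted from a published toxicity index.
- Sections 14.6 and 14.7 collect adverse events at telephone and clinic contacts and give infection as an example of glucocorticoid toxicity. They do not define it.

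**The concern.** Infection bears on both sides of the benefit-harm balance. Section 5.3 says that steroids carry "a dose-dependent increased risk of infection". Section 5.4 reports small numerical increases in infectious adverse events on methotrexate in a large placebo-controlled trial, though no increase in serious infections. Section 5.6 argues for steroid-sparing partly on the risk of severe COVID-19. A trial built on that trade-off needs a stable count of infections.

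The item sorts infections by class of drug given and, for COVID-19, by where the test was done. A COVID-19 case first detected in hospital can fall outside it while a mild community case may fall inside. Because the header and two of the limbs disagree, two sites could handle the same mild case differently and both claim to follow the protocol. Infections not recorded during follow-up may be hard to recover later.

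**Working it through.** The protocol states no infection rate, count or power that depends on this definition, so there is no figure to reproduce. The check is to trace types of infection through each rule. Treating mild shingles or a symptom-free positive test as below grade 2 is an assumption, since the grade text is not in the protocol.

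| Case | Infection item, 15.2.2/15.2.3 | Grade 2 header | SAE route under 15.3 | SAE route under 16.2.2 |
|---|---|---|---|---|
| Non-serious infection treated only with an antiviral or antifungal; not shingles, not community-test COVID-19 | No limb met | Immaterial | Not serious | Not serious |
| COVID-19 first detected in hospital, no antibiotics, causing or prolonging the stay | No limb met | Immaterial | Only if suspected related to PMR or a DMARD | Counted |
| Admission for another viral or fungal infection, no antibiotics | No limb met | Immaterial | Only if suspected related | Counted |
| Mild shingles | Met | Not met | Not serious | Not serious |
| Symptom-free positive community COVID-19 test | Met | Not met | Not serious | Not serious |
| Severe shingles, or severe COVID-19 with a positive community test | Met | Met | If serious and suspected related | If serious |
| Infection given oral, IV or IM antibiotics, in any setting | Met | Met if grade 2 or above | If serious and suspected related | If serious |

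Four things follow.

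1. **Gap.** Rows 1 to 3 meet no limb at any grade. Row 1 has no SAE route either. It is captured only if the undefined infection entries in 14.6, 14.7 and 16.2.2 are read to include it.
2. **Conflict.** In rows 4 and 5 the item says report and the header says do not. A limb that takes every shingles episode, or a bare test result, has no severity threshold, so the conflict shows in the wording without the CTCAE text.
3. **Backstop.** For rows 2 and 3 the two SAE rules give different answers when the event is judged unrelated. Section 15.4.1 asks for all SAEs to be recorded but does not say whether that means all as defined in 15.1 or only those kept by 15.3.
4. **Possible imbalance.** Section 12.2 names only methotrexate and leflunomide as IMPs. Under 15.3 a hospitalised infection in a usual-care participant who has taken no DMARD is reportable only if attributed to PMR. In the DMARD arm it can also be attributed to the DMARD. The trial is open-label (7.1), so the relatedness filter could act differently by arm. The documents do not show that it will.

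**The case against.** The strongest reply is that the item is not the only route. A hospitalised or life-threatening infection is an SAE whatever the organism, and 16.2.2 counts SAEs regardless of relatedness. Infection is an expected event for both DMARDs, so a related judgement is plausible. Telephone and clinic contacts ask about infection with no antibiotic condition. This stands to the extent that a reader might infer that severe viral or fungal infections go uncounted, and the documents do not support that. Severe shingles and severe community-test COVID-19 are within the item, and serious infections have a route, though a contradictory one. Nor does the item drop all hospital infection: the antibiotic limb has no setting limit, and only the COVID-19 test is tied to the community. The protocol also does not say that the glucocorticoid-toxicity outcome uses this item, so an under-count there cannot be asserted. Equally, no other operational definition of infection is given for that outcome.

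A second reply is that header and item can be read together: the event must fit the description and reach grade 2. That reading is possible, but it leaves little meaning in a limb that takes every shingles episode, and the protocol does not choose it.

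A third is that antibiotic treatment is a simple, verifiable threshold that the protocol already uses when DMARD interruption is considered (7.5.2, 13.1.17). That is a reason to keep the limb, not to leave out the others.

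A fourth is that widening the item guarantees that mild COVID-19 is counted. It does. With the grade recorded, mild and severe cases can be separated, which a disputed filter does not allow.

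**Conclusion.** The point holds as a definitional gap and an internal conflict. It is a cheap improvement, not a flaw that undermines the trial. The gap consists of infections treated only with antivirals or antifungals (other than shingles and community-test COVID-19) and COVID-19 first detected in hospital without antibiotic treatment. The conflict is between the grade 2 header and the shingles and COVID-19 limbs. The SAE route narrows the gap for serious infections but is unreliable while 15.3 and 16.2.2 disagree.

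No size can be put on the under-count. A reader might assume, for example, a 40% risk of infection over 18 months with 10% to 25% of infections outside the item, and infer an observed risk of 0.40 × 0.90 = 36% to 0.40 × 0.75 = 30%. None of those inputs is in the documents. The product also treats a lost infection as a lost participant: anyone who also has a qualifying infection is still counted, and the SAE route is ignored. Section 18.3 reports adverse events descriptively, by treatment received and severity, so a diluted difference between arms is not a stated analysis either. The conclusion rests on the wording alone. Its one assumption is that some shingles episodes or positive tests would be graded below 2.

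**What to change.** Make four changes to the protocol.

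1. In 15.2.2 and 15.2.3, define infection as any of: an infection requiring systemic antimicrobial treatment (antibacterial, antiviral or antifungal) or hospital admission; any shingles; a positive COVID-19 test in any setting.
2. State that this item is exempt from the grade 2 header and is reported at every grade, with the CTCAE grade recorded so that results can be shown by severity, as 18.3 intends.
3. State in 16.2.2 that the same definition serves the infection component of glucocorticoid toxicity, and refer to it from 14.6 and 14.7.
4. Reconcile 15.3 with the Safety paragraph of 16.2.2, so that sites have one rule on whether SAEs judged unrelated are reported, and align 15.4.1 with it.

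The cost is an edit to the adverse event guidance and an eCRF label, and slightly more events to record. Treatment does not change.
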